8.4.2.3 Vital Signs

Vital signs will be measured at all clinic visits as outlined in Table 1. Vital signs include body temperature, heart rate, respiratory rate, and blood pressure. All vital signs will be obtained after the patient has been resting for at least 5 minutes.

Weight will also be measured at all clinic visits as part of physical examinations (see Section 8.4.2.6).

For the first infusion of MPDL3280A, vital signs should be measured within 60 minutes before, every 15 (\pm 5) minutes during the infusion, and 30 (\pm 10) minutes after the infusion. For subsequent infusions, vital signs will be collected within 60 minutes before the infusion, during the infusion if clinically indicated or if symptoms occurred in the prior infusion, and 1 hour (\pm 10 minutes) after the infusion.

8.4.2.4 12-Lead Electrocardiograms

Triplicate serial 12-lead ECGs (10-sec ECG tracings collected in triplicate > 2 min apart) will be taken at time points specified in Table 1 and as clinically indicated. The average of triplicates should be recorded.

Electrocardiograms should be performed after the patient has been resting for at least 5 min. The 12-lead ECGs collected will be read locally to facilitate patient management and analyzed at a central ECG laboratory. Details on recording ECGs and their interpretation will be included in the Investigator's file.

8.4.2.5 Echocardiogram (ECHO) or Multigated Acquisition (MUGA) Scan

An ECHO or MUGA scan will be performed at screening only for patients with a known history of pericardial effusions, or for whom the Investigator suspects has the potential for a pericardial effusion, and otherwise as clinically indicated.

8.4.2.6 Physical Examinations

Physical examinations will be performed at every clinic visit as outlined in Table 1.

Complete physical examinations will include height (at screening only), weight (the patient should be in light indoor clothes; no shoes), and the evaluation of head, eyes, ears, nose and throat (HEENT) and cardiovascular, dematologic, musculoskeletal, respiratory, gastrointestinal, and neurologic systems.

Limited physical examinations will include weight, an assessment of all baseline abnormalities and recording of associated changes, questioning of the patient about any skin or vision changes, and any other symptom-directed examination.

8.4.2.7 ECOG Performance Status

ECOG performance status (Appendix C) will be assessed at time points specified in Table 1. ECOG performance status should be assessed by the same study personnel at each visit, if possible. Care will be taken to accurately score performance status, especially during screening for study eligibility purposes. Additional consideration should be given to borderline ECOG performance status to avoid enrolling patients with significant impairment.

8.4.2.8 Pulmonary Function Tests

Patients are required to have a pulmonary function evaluation conducted at baseline and as clinically indicated. Pulmonary function tests must include an assessment of DLCO.

8.4.3 Efficacy Evaluations

8.4.3.1 Tumor Assessments

Tumor assessments will be performed at screening and during the Treatment Period until permanent discontinuation of all study treatment (patients who continue treatment with rociletinib and/or MPDL3280A after a radiographic progression should continue to be scanned according to the protocol until they permanently discontinue all study treatment).

The frequency of tumor assessments will be every 2 cycles (6 weeks ± 1 week) through Cycle 6 (ie, at the end of Cycles 2, 4, and 6); every 3 cycles (9 weeks ± 1 week) after Cycle 6 (ie, at the end of Cycles 9, 12, etc); and at the EOT Visit. The frequency of tumor assessments may be further reduced after 2 years with the approval of the Medical Monitor. Tumor assessments at the EOT Visit are not required if radiographic disease progression has been documented previously or the last tumor assessments were performed < 2 weeks before the last dose of study treatment. If an initial complete response (CR) or PR is noted, confirmatory scans must be performed 4 to 6 weeks later.

Scans will be evaluated locally for response evaluation and patient treatment decisions. Tumor response will be evaluated using RECIST v1.1 (Appendix A) and modified RECIST incorporating irRC (Appendix B).

Tumor assessments should consist of clinical examination and appropriate imaging techniques (preferably CT scans of the chest, abdomen, and pelvis with ≤ 5 mm slice thickness); other studies (MRI and X-ray) may be performed if required. Brain imaging is required at baseline. Patients with brain lesions at baseline will require repeat brain imaging as part of the follow-up tumor assessments. Patients without baseline brain lesions do not require brain imaging on study unless clinically indicated. The same methods used to detect lesions at baseline are to be used to follow the same lesions throughout the clinical study.

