	Tumor assessments will be conducted for the duration that the patient is on study treatment (Section 8.4.3.1). In addition, patients will provide blood samples for PK and pharmacodynamics/biomarker assessments at protocol-defined time points (see Table 2).							
	During a Follow-up Period, patients will be followed for adverse events through 28 days after last dose of study treatment, or until initiation of subsequent anticancer therapy, whichever is earlier. Patients will also be contacted approximately every 3 months for collection of data on subsequent anticancer treatment and survival. In addition, the patient will be asked to return 120 days after the last dose of MPDL3280A to collect samples for pharmacokinetic (PK) and anti-therapeutic antibody (ATA) samples (see Table 2).							
	See the Table 1 for detailed study procedures.							

DIZ	
РК	Please refer to Table 2 for a detailed PK sampling schedule.
	On scheduled PK sampling days, patients should be instructed to not self-administer study drug at home, but to bring rociletinib to the clinic along with breakfast. After a predose PK blood draw, patients will eat breakfast and take the morning dose of rociletinib within 30 minutes after starting their meal. On days of MPDL3280A infusions, patients will be administered IV MPDL3280A approximately 2 hours after the morning rociletinib dose. Times of the meals and administrations of study drugs in the clinic should be recorded. Additional unscheduled PK blood samples will be collected at the time of fresh tumor biopsy and may also be collected when a patient experiences an adverse event for which the Investigator would like to have PK data to help understand the safety observation.
Pharmacody-	Please refer to Table 2 for a detailed pharmacodynamic blood sampling schedule.

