8.3 Follow-Up Period

During the Follow-Up-Period, all patients will be contacted by the site every 12 weeks $(\pm 1 \text{ week})$ for the collection of information on all subsequent anticancer therapy and for the monitoring of survival status until the patient's death, patient withdrawal of consent, or a decision by the Sponsor to cease data collection and close the study, whichever comes first. These assessments may be performed during routine clinic visits or by telephone contact.

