10.2.4.2.4 Progression-Free Survival (PFS)

Progression-free survival (PFS) will be calculated as 1+ the number of days from the first dose of study drug to documented radiographic progression, as determined by the Investigator or death due to any cause, whichever occurs first. Patients without a documented event of radiographic progression will be censored on the date of their last adequate tumor assessment (ie, radiologic assessment) or date of first dose of study drug if no tumor assessments have been performed.

For patients who continue treatment post-progression, the first date of progression will be used for the analysis of PFS.

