11 PATIENT DISPOSITION

11.1 Permanent Discontinuation of Study Treatment

A patient must be discontinued from all study treatment if any of the following applies:

- Consent withdrawal at the patient's own request or at the request of their legally authorized representative;
- Clinical disease progression where the Investigator believes that the patient will not continue to benefit from study treatment (*Note:* patients will be permitted to continue study treatment after a radiographic progression [Appendix A: and Appendix B] if the benefit-risk ratio is judged to be favorable and continued treatment is approved by the Medical Monitor);
- Any event, adverse or otherwise, that, in the opinion of the Investigator, would pose an unacceptable safety risk to the patient;
- Any requirement for dose holds of rociletinib for more than 14 days or dose holds of MPDL3280A for more than 42 days, unless permission from the Sponsor's Medical Monitor for longer dose delay is granted;
- An intercurrent illness that, in the opinion of the Investigator, would affect assessments of the clinical status to a significant degree and requires discontinuation of therapy;
- A positive pregnancy test at any time during the study;
- Investigator decision.

In addition, the Sponsor may discontinue the study early for any of the reasons noted in Section 12.6.

The Sponsor (or designee) should be notified of all study terminations as soon as possible. The date and reason for cessation of PO rociletinib and/or IV MPDL3280A must be documented in the eCRF and source documents.

To the extent possible, EOT assessments should be performed for all patients who receive rociletinib and MPDL3280A. The EOT visit should occur 28 (\pm 7) days after the last dose of rociletinib and MPDL3280A. After stopping protocol-specified treatment, all patients will remain in the study and will be followed for safety (through 28 days after last dose; those with ongoing SAEs will be followed until either resolution or stabilization has been determined), for disease progression (every 8 \pm 1 weeks until disease progression), and for survival status and subsequent NSCLC therapies (at approximately quarterly intervals until death or Sponsor decision).

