PR	PD	SD provided minimum criteria for SD duration met, otherwise, PD
PR	NE	SD provided minimum criteria for SD duration met, otherwise, NE
NE	NE	NE

CR, complete response; PD, progressive disease; PR, partial response; SD, stable disease; NE, Not evaluable.

a If a CR is truly met at first time point, then any disease seen at a subsequent time point, even disease meeting PR criteria relative to baseline, makes this disease PD at that point (since disease must have reappeared after CR). Best response would depend on whether minimum duration for SD was met. However sometimes 'CR' may be claimed when subsequent scans suggest small lesions were likely still present and in fact the patient had PR, not CR at the first time point. Under these circumstances, the original CR should be changed to PR and the best response is PR.

Missing Assessments and Not Evaluable Designation

When no imaging/measurement is done at all at a particular time point, the patient is not evaluable (NE) at that time point. If only a subset of lesion measurements are made at an assessment, usually the case is also considered NE at that time point, unless a convincing argument can be made that the contribution of the individual missing lesion(s) would not change the assigned time point response, which is most likely to occur in the case of PD; eg, if only 2 of 3 baseline target lesions are assessed and result in a > 20% increase in the sum, then the patient would be assessed as a PD regardless of the missing lesion.

Patients with a global deterioration of health status requiring discontinuation of treatment without objective evidence of disease progression at that time should be classified as having symptomatic deterioration. Every effort should be made to document the objective progression, even after discontinuation of treatment.

In some circumstances, it may be difficult to distinguish residual disease from normal tissue. When the evaluation of CR depends on this determination, it is recommended that the residual lesion be investigated (fine needle aspiration/biopsy) before confirming the CR status.

Confirmatory Measurement/Duration of Response

Confirmation

Radiographic tumor assessments are required every 6-9 weeks (see Table 1). If an initial CR or PR is noted, confirmatory scans must be performed 4-6 weeks later. In the case of SD, follow-up measurements must have met the SD criteria at least once after study entry at a minimum interval of no less than 4 weeks.

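### Section 11.1 follows patients for progression after treatment stops, but the synopsis, Table 1 and Section 8.4.3.1 end tumor assessments by the EOT Visit, so PFS and DOR for patients who stop without progression depend on which text a site follows

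*Combined protocol and SAP*

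**What the plan says.** **Texts that end tumor assessments with treatment**

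- Section 8.4.3.1: "Tumor assessments will be performed at screening and during the Treatment Period until permanent discontinuation of all study treatment". Scans fall every 6 weeks through Cycle 6, then every 9 weeks, with one more at the EOT Visit. The EOT scan is waived if radiographic progression is already documented or the last scan was less than 2 weeks before the last dose.
- Synopsis, Study Procedures: "Tumor assessments will be conducted for the duration that the patient is on study treatment".
- Table 1 and footnote W: same schedule, ending at the EOT Visit. The Follow Up column holds only MPDL3280A PK, ATA and survival/subsequent therapy.
- Section 8.2.2 places the EOT Visit 28 (+7) days after the last dose, or before a new anticancer agent if that comes sooner.
- Section 8.3: contact every 12 weeks "for the collection of information on all subsequent anticancer therapy and for the monitoring of survival status". Table 6 likewise shows no progression follow-up after treatment.

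**Text that continues**

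- Section 11.1: "After stopping protocol-specified treatment, all patients will remain in the study and will be followed for safety". The same sentence adds checks for progression at 8-week intervals (± 1 week), which end only when the disease progresses.

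**Endpoint definitions**

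- PFS (Section 10.2.4.2.4) runs to "documented radiographic progression, as determined by the Investigator or death due to any cause, whichever occurs first". Patients without a progression event are censored at the last adequate tumor assessment.
- DOR (Section 10.2.4.2.2) runs to objectively documented progression and is otherwise censored at the most recent tumor assessment. Death is not listed as a DOR event.

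**The concern.** The patients affected are those who stop both drugs without radiographic progression. Section 11.1 foresees several routes to this: an unacceptable safety risk, an over-long dose hold, intercurrent illness, clinical progression without a radiographic event, or a decision by patient or investigator. For them the plan gives two follow-up rules that cannot both be followed, and no other passage chooses between them.

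Both endpoints are censored at the last tumor assessment, so the rule in use fixes the censoring date and decides whether a later progression can be seen. If reasons for stopping are related to prognosis, censoring at EOT is informative. If sites read the protocol differently, follow-up also differs by site. Scans not taken off treatment cannot be recovered later.

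**Working it through.** **1. The passages side by side, for a patient who stops all treatment without radiographic progression**

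| Place | Last tumor assessment | Interval after stopping |
|---|---|---|
| Synopsis | while on treatment | none |
| 8.4.3.1; Table 1, footnote W | EOT Visit, unless waived | none |
| 8.3; Table 6 | not mentioned | 12-weekly survival and therapy contact |
| 11.1 | progression | 8 ± 1 weeks |

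The 8-week interval matches neither the 6-week nor the 9-week on-treatment interval. Section 11.1 does not name imaging, but PFS needs radiographic progression and DOR needs objective documentation, so follow-up without scans could not supply either endpoint.

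**2. What each rule does to the endpoints**

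Let the last dose be on day t, with a clear EOT scan on day t + 28. Progression then occurs at time p, and death, if observed, at time d > p.

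| | Scans end at EOT | Progression follow-up per 11.1, with imaging |
|---|---|---|
| PFS, alive at cut-off | censored at t + 28 | event at first scan after p |
| PFS, died | event at d | event at first scan after p |
| DOR, alive or died | censored at t + 28 | ends at first scan after p |

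If the EOT scan is waived, the last on-treatment scan replaces t + 28. Under the EOT rule the progression at p is never seen. Survival follow-up still finds the death, which enters PFS late. For DOR the responder is simply censored.

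**3. Size**

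The plan gives no event count, power or discontinuation figure for PFS or DOR, so there is nothing to reproduce. The following are illustrations only.

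Inputs from Section 1: median PFS 10.4 months (rociletinib monotherapy) and median post-progression survival 1.9 years = 22.8 months (T790M+). Assumptions: exponential times, a fraction f = 10 to 30% stopping before progression, progression hazard off drug 1 to 3 times that on drug, and a 24-month cut-off.

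Progression hazard λ = ln 2 / 10.4 = 0.0667 per month. Stopping hazard μ = λf/(1 − f); for f = 0.3, μ = 0.0667 × 0.3/0.7 = 0.0286 per month.

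Median PFS in months, scans ending at the stop minus scans to progression (no scan grid, no EOT scan):

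| f | hazard ×1 | ×2 | ×3 |
|---|---|---|---|
| 10% | 10.4 − 10.3 = 0.1 | 10.5 − 10.1 = 0.4 | 10.5 − 9.9 = 0.6 |
| 20% | 10.6 − 10.4 = 0.2 | 10.6 − 9.8 = 0.8 | 10.5 − 9.4 = 1.1 |
| 30% | 10.7 − 10.4 = 0.3 | 10.7 − 9.4 = 1.3 | 10.6 − 8.9 = 1.7 |

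Adding a scan one month after stopping brings the first median in the extreme cell (30%, ×3) down to 10.1, a gap of 10.1 − 8.9 = 1.2. Suppose imaging also ends, with PFS censored, at new therapy starting a median of 1 to 4 months after stopping (assumption). The comparator is then 9.3 to 9.8 and the gap 0.3 to 0.8. With hazard ×1 that gap is 0.1 to 0.2.

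A second run used the actual scan calendar, an EOT scan at 4 weeks, 8-weekly scans thereafter, a 36-month cut-off and 12 months' median survival after progression (assumption). Medians differed by 0 to about 2 months. That spread is about one scan interval: the scans at weeks 45 and 54 fall at 10.3 and 12.4 months, and the assumed median lies just after the first, so the Kaplan-Meier median flips between them. Event capture is the steadier reading: 82 to 90% of patients had a PFS event with scans ending at EOT, against 90 to 96% with scans to progression. The gap runs from 92.0 − 89.6 = 2.4 to 90.5 − 81.9 = 8.6 percentage points.

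**4. Precision for comparison**

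Under the same exponential model without censoring, the standard error of a median is about 1/(λ√n). With 1/λ = 15.0 months this is 15.0/√25 = 3.0 months in Group A and 15.0/√50 = 2.1 months in Group B.

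**The case against.** The case for giving this little weight is substantial. PFS and DOR are summarized by Kaplan-Meier only (Section 10.2.1), no comparison between groups or subgroups is planned (Section 10.2.4.2.6), and the sample-size and futility reasoning uses response rate alone (Section 10.3). The illustrated shifts in the median are smaller than its standard error. Section 5.7.4 lets a patient who stops one drug for toxicity continue the other, and such a patient stays on the scan schedule, so the affected group may be small. All of this stands, and it lowers the priority. It does not remove the conflict between the two rules.

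Some stronger readings are tempting and not supported:

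- *That sites will follow Table 1 and the Section 11.1 follow-up will not happen.* The documents do not show which text sites will use. The problem is that either is possible.
- *That no scan follows treatment.* The EOT scan does, unless waived, and it sets the censoring date.
- *That PFS is overstated by a known amount.* If progression is no faster off drug, the median barely moves. The larger figures come from an assumed two- to three-fold hazard.
- *That Appendix A asks for imaging after any discontinuation.* Its sentence, "Every effort should be made to document the objective progression, even after discontinuation of treatment", concerns symptomatic deterioration. It adds to the inconsistency for those patients, not for patients who stop for toxicity or by choice.
- *That Section 11.1 already prescribes scans up to new therapy.* It names neither imaging nor a stop at new therapy.

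**Conclusion.** The contradiction is real, and nothing else in the document resolves it. For patients who stop all treatment without radiographic progression, the PFS and DOR censoring date and the counting of later progressions are undetermined.

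The size depends on a rate of stopping without progression and an off-drug hazard that the documents do not give. Under the stated assumptions the effect on median PFS lies between near zero and about 1 to 2 months at the extreme, with 2 to 9 percentage points fewer PFS events captured. It is smaller if follow-up stops at new therapy. DOR was not quantified; its direction is later progressions lost to censoring.

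A reader might infer that the trial's main conclusions are at risk. They are not: response rate and the futility rules are little affected. This is a should-fix, best made before data accrue.

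**What to change.** Reconcile Section 11.1, the synopsis, Table 1 (Follow Up column and footnote W), Table 6, Section 8.3 and Section 8.4.3.1 to one rule:

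- Keep Section 11.1's commitment. State that patients who stop all study treatment without RECIST progression continue tumor imaging until progression, at one stated interval.
- State whether imaging also ends at death, withdrawal of consent or the start of subsequent anticancer therapy.
- Give Sections 10.2.4.2.2 and 10.2.4.2.4 a censoring rule for subsequent therapy that matches.

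Ending imaging and censoring at new therapy recovers only part of the gap, so that choice should be made knowingly.

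The cost is protocol wording and a few off-treatment scans in patients who stop before progression.

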8.4.4 Pharmacokinetic Evaluations

Blood samples for PK profile analysis of rociletinib (and its metabolites) and MPDL3280A, will be collected at visits and time points described in Table 1 and Table 2. Central laboratories will be used for bioanalysis of these samples. Please refer to the laboratory manual for details on collection and processing of blood PK samples.

On scheduled PK sampling days, patients should be instructed to not administer study drug at home, but to bring rociletinib to the clinic along with breakfast. After a predose PK blood draw, patients will eat breakfast and take the morning dose of rociletinib within 30 minutes after starting their meal. On days of MPDL3280A infusions, patients will be administered IV

MPDL3280A approximately 2 hours after the morning rociletinib dose. Times of the PK blood draws, meals, and administrations of study drugs in the clinic should be recorded.

Additional unscheduled PK blood samples will be collected at the time of fresh tumor biopsy and may also be collected when a patient experiences an AE for which the Investigator would like to have PK data to help understand the safety observation.

8.4.5 Pharmacodynamic Evaluations

A mandatory fresh tumor tissue biopsy specimen will be collected within 60 days prior to the first day of study treatment for all patients. In addition, an optional fresh tumor biopsy may be collected at time of disease progression (or patient is considered by the Investigator to no longer benefit from study treatment, if treatment is continued beyond a radiographic progression).

The baseline tissue biopsy specimen from screening will be used for a retrospective confirmation of EGFR mutation status by a central laboratory. The baseline biopsy as well as the optional tissue biopsy collected at disease progression will also be used to investigate mechanisms of response, primary resistance, and acquired resistance to rociletinib and MPDL3280A. Immunohistochemistry (IHC) using exploratory biomarkers of the EGFR and PD-L1 pathway signaling such as PD-L1, CD8, and MHC Class II may be performed. Samples may also be assessed for genomic alterations (eg, mutations, amplifications, and fusions) in a panel of established cancer genes by next generation sequencing (NGS). A subset of specimens may also be characterized using additional genomic (whole exome), transcriptional (whole transcriptome, RNA-Seq), or protein-based approaches.

Blood samples will be collected for pharmacogenomic and pharmacodynamic analyses to investigate mechanisms of response, primary resistance, and acquired resistance to rociletinib and MPDL3280A. The pharmacogenomic blood sample will be collected predose on Day 1 of the Run-in-Period for Phase 1, and on C1D1 of Phase 2 for genomic DNA purification. The DNA sample may be evaluated by NGS, and molecular alterations in germline and tumor DNA may be compared so that molecular alterations unique to the tumor can be unambiguously identified. Pharmacodynamic blood samples will be collected as outlined in Table 2.

Pharmacodynamic blood samples will be processed to plasma and/or serum and PBMCs to evaluate markers which may include (but are not necessarily limited to) IGF-1, insulin, c-peptide, and T-cell receptor diversity. Cell-free DNA will be purified from plasma samples and evaluated for EGFR mutation status and possibly also for similar DNA analyses as described for tumor biopsies (eg, targeted cancer panel NGS), if sufficient DNA is available.

Changes in biomarker status will be investigated for associations with rociletinib and/or MPDL3280A exposure, safety, and clinical activity.

Please refer to the Laboratory Manual for details on collecting and processing pharmacodynamic samples.

